- **Patient education on hypertension, cardiovascular risk reduction & stroke:** PINGSTERs will receive audio and text messages delivered in the preferred local dialect once a week on HTN/stroke facts and importance of medication adherence. Sample of messages include “reducing the intake of salt, eating vegetables& fruits will help keep your blood pressure controlled”. The SMS text and/or audio messages on HTN/stroke are intended to improve health literacy on stroke and its risk factors. SMS messages will be sent in English language, *however for participants who cannot read or speak English, audio messages in their preferred native language will be sent instead*. The mHealth intervention in PINGS II will be delivered by Viamo Technologies Limited®. Viamo is a local Ghanaian company with presence in 22 countries specializes in using mHealth technology to drive behavior change in LMICs. Viamo will use SMS and local-language interactive voice response (IVR) messages using in-house algorithms to disseminate hypertension behavior change messages and medication reminders to participants on **basic feature phones** with the objective of increasing self-efficacy. (see letter of support).

E.4.5.2. Provider Level: Providers will follow care protocols based on expert consensus practice guidelines to address HTN management. A task-shifting strategy using nurse navigators will be used in this study to deliver primary care to stroke patients with HTN. Male and female nurse navigators will be recruited and trained for this study. The Nurse navigators will receive approximately 80 hours of intensive training over a 2 week period prior to initiating study at each study site. They will participate in didactic and group-based learning on the fundamentals of non-communicable diseases, health promotion/disease prevention and patient centered communication. They will receive instructions on how to reinforce patient adherence to antihypertensive regimens through patient- and family-centered approaches & also receive training on proper BP measurement technique. If a PINGster's mean BP exceeds thresholds (e.g., BP >180/ 105 or <100/75 mmHg), the patient will contact the **nurse navigator** via a phone call or text message for advise on what to do. The nurse navigator will follow an algorithm to address issues relating to non-adherence, side effects, insufficient dosing of antihypertensive med, and so forth. In instances where a clinic visit is required to address BP threshold breeches or health related issues, the nurse navigator will arrange with the research team to have patient seen.

E.4.6. Usual care Protocol: Inclusion criteria include owning a cell phone with at least SMS and voicemail. To control for attention exposure, they will get SMS messages dealing with healthy lifestyle behaviors (smoking, diet, physical activity) but not with med adherence, HTN or stroke related issues. Similar to the intervention group, the usual care patient will have a total of 5 follow-up study visits during which various study outcomes (see Figure 1) will be assessed. Usual care participants will also be contacted by phone monthly to confirm contact information and to inquire about hospitalizations.

E.4.7. Health care access during and after intervention: Both during and after the intervention, study participants will be followed up at the study sites at scheduled visits for evaluation of study outcomes and have access to the study physicians for *unscheduled visits for any health urgencies or emergencies, in particular where BP breeches require hospitalization for urgent management*.

E.4.8. Outcome and Mediator Measures: Primary outcome is proportion of participants with BP<140/90mmHg at 12-months which is the major modifiable step to stroke event rate reduction. We will also conduct longitudinal comparisons of systolic BP in the intervention vs. usual care groups over the course of follow-up evaluations. Participants will be given an appointment encounter solely for collecting evaluation data at the times listed in Figure 1. Trained assessors with no contact to the PINGS study team will perform all study measurements. Potential mediator/moderators of risk factor control and implementation outcomes will also be collected.

E.4.8.1. Physiological/Laboratory Measures

i. BP measurements: Three readings will be taken by trained study coordinators using an automated BP monitor with the patient seated comfortably for 5 min prior to the measurements, following guidelines.^{174,175} Average of the last 2 BP readings will be used as the measure for each visit. Uncontrolled BP is defined as average clinic systolic BP \geq 140 mm Hg or diastolic BP \geq 90 mmHg per guidelines.¹⁷⁶

E.4.8.2. Self-report Measures and Other Information: Self-report measure outcomes will be assessed using validated questionnaires (see Table 3) administered by trained Research Assistants blinded to allocation of study participants to record responses of participants.

Table 3. PINGS-2 Outcomes and Mediators

| Outcomes | Brief Description |
|---|---|
| Systolic Blood Pressure (Primary outcome) | Target goal of <140/90 mmHg measured at baseline, months 3, 6, 9 and 12. Measured by blinded evaluator using an automated BP monitor. |

| | |
|--|---|
| Self-management outcome (Secondary outcome) | Compared between the two groups using the validated Hypertension Self-care Profile questionnaire (HBP SCP) with items that compositely assesses behavior, motivation and self-efficacy of hypertension management. Assessed at months 4, 8 and 12 ($\alpha=.83-.93$, $r=.64$) ¹⁸¹ |
| Medication adherence (Secondary outcome) | Measured using Medication possession ratio ¹⁷⁷ and 14-item Hill-Bone compliance (HBC) to high blood pressure therapy scale with items that assess medication adherence, clinic appointments and salt intake ¹⁷⁸ assessed at months 3, 6, 9 and 12 ($\alpha=.76-.83$, $r=.64$) ^{179,180} MPR and HBC will be measured in both PINGS and usual care arms at stated time points. |
| Cardiovascular ED encounters and re-hospitalizations (Secondary outcome) | To be assessed via once monthly calls to patients and/or carers over 12 months of follow up in both the PINGS and usual care groups. Patient carers in both arms will also be encouraged to contact study team within 48 hours of hospitalizations for prompt and blinded adjudication of all potential CVD ED encounters to minimize reporting bias between the two groups. |
| Major Adverse Cardiovascular Events (Secondary outcome) | Major Adverse Cardiovascular events (MACE) to be assessed include recurrent stroke: fatal/ severely disabling stroke or non-fatal stroke; Co Disease: Acute STEMI/NSTEMI, sudden cardiac deaths. MACE will be confirmed by a blinded adjudicator by reviewing where available clinical notes supported by investigations e.g. CT scan, EKGs, review of death certificates or verbal autopsy if death occurs outside hospital. |
| Health Literacy in HPT/stroke (Mediator) | Self-Report: HTN/stroke Knowledge questionnaire ($r=.70$), ^{182,183} Health literacy questionnaire ($r=.74, .82$), ^{184,185} Assessed at months 0, 6, 12. |
| Health-related quality of Life (secondary) | The EQ-5D questionnaire, ¹⁸⁶ will assess state of health of study participants at baseline and Month 12. |
| Disability/Functional status (Mediator) | Functional status after stroke will be assessed by Research Assistants using the Modified Rankin Scale ^{187,188} with a scores ranging from 0 to 6, where 0=no functional limitation and 6 = death. Assessed at months 0, 3, 6, 9 and 12. |
| Sex, Age, cultural, socio-economic Factors, study site (mediator) | Assessed based on self reports at baseline. Cultural factors to assess include language spoken at home, religious observances, acceptance of gender roles; occupation, religious beliefs and dietary practices. |
| Side effects, Adverse events | As reported by participants during follow-up using NCBI toxicity criteria |

E.4.8.3. PINGS Intervention Implementation Outcomes: Among the 250 subjects assigned to the PINGS intervention, we will use surveys, qualitative or semi-structured interviews, checklists to assess **six (6)** implementation outcomes proposed by Proctor et al¹⁸⁹ namely (i) **acceptability** (satisfaction with content, complexity, comfort, delivery and credibility of PINGS); (ii) **adoption** (uptake, utilization, intention to try, refusal rates); (iii) **appropriateness** (perceived fit, relevance, compatibility, usefulness); (iv) **feasibility** (suitability for everyday use, practicability); (v) **fidelity** (use checklist to assess whether PINGS was delivered as intended, quality of program delivery); (vi) **implementation cost** (marginal costs of the intervention & delivery strategy). Furthermore, among providers across the 10 study sites, we will assess provider satisfaction level (e.g. assess provider fatigue from breaches in BP thresholds) using Healthcare provider satisfaction questionnaire.¹⁹⁰

E.4.9. Statistical Considerations

E.4.9.1. Randomization: Once eligibility, consent & baseline data are confirmed, participants will be randomly assigned to PINGS intervention vs. usual care in a 1:1 allocation ratio, stratified by study site. An adaptive block randomization scheme will be developed & maintained by the lead study biostatistician. Once a patient is randomized he or she will be entered into the study and included in intent-to-treat analysis. The randomization assignment will be known to the project coordinator, and the statistician in charge of the randomization procedure, but not known to the research assistant who will be conducting participant follow-up assessments.

E.4.9.2. Power and Sample Justification: Our sample size calculation and power analyses are based on the proportion with BP<140/90mmHg at 12 months, the premier modifiable risk factor for stroke. In a recent pilot study^{44,45} by this group in Ghana, where this proposed study will take place, 60 subjects (30 per group) were randomized to PINGS & control arms with BP<140/90 mmHg at month 9 was 46% versus 40% after withdrawing the PINGS intervention after 3 months.⁴⁵ We anticipate at least 60% BP control rate in the intervention arm (lasting for 12 months) versus 44% control in the usual care arm, using a type I error of 0.05, a power of 90%, & a two-sided test, we need a total of 406 subjects. Assuming 20% loss to follow up, the conservative target for enrollment is 500. We conservatively expect ~50% will not meet eligibility criteria or may decline to participate, so we can potentially recruit over 500 patients from ~ 5,550 stroke patients encountered at 10 hospitals over 4 years.

E.4.10. Data Management and Analysis

E.4.10.1. Analysis: Descriptive statistics will be computed for all study variables, including average follow-up time, retention rate, protocol deviations and violations, and will be compared by treatment group. We will use t-test (Wilcoxon rank sum test) for continuous variables and chi-square test for categorical variables to make comparisons between two groups. The primary analysis will be performed according to the principle of intention to treat. However, we will also do per-protocol sensitivity analysis. All outcomes will be modeled using regression analyses adjusted for baseline factors that show imbalance after randomization and compared to analysis that does not adjust for residual baseline differences.^{192,193} A nominal p value of 0.05 or less will be considered as statistically significant in the primary analysis. A linear mixed model with the 12-month outcomes as dependent variable and baseline value as a covariate will be used to test the hypotheses in Aims 1 and 2 adjusting for other baseline covariates that show imbalance. Assessment of the fit of the models will be made using residual and diagnostic plots. We will employ longitudinal data methods (generalized linear mixed models [GLMM]),¹⁹⁴ which account for correlation of outcomes due to repeated measurements & missing at random (MAR) data to study the change in outcomes over time between the two groups. We will model binary (logit link& binomial distribution) and count outcomes (log link and poisson or negative binomial

distribution) by properly selecting the link and distribution option of the GLMM. In addition, to evaluate sensitivity of study conclusions to missing data, we will use both last value carried forward& multiple imputation methods to estimate single end-point outcome measures and carry out analyses on the complete data set. We will also use the MNAR statement in SAS 9.4 to make sensitivity analysis on the MAR assumption. If we suspect violation of MAR then we will report the most plausible sensitivity analysis results.¹⁹⁵ Trajectory of BP and other related outcomes will be modeled via GLMM. Differences in time to recurrent events between the two groups will be compared using a log-rank test & a Cox proportional hazards (PH) model (we will test for the PH assumption) will be used to adjust for observed confounders& for clustering via frailty models. Additional analyses will assess patients' adherence to intervention and **biological variables, in particular, age of participants, sex (male versus female), cultural, socio-economic and family factors on primary and secondary outcomes such as self-management, medication adherence outcomes.** We will adjust self-reported measures for potential measurement error using standard techniques.¹⁹⁶

E.4.10.2. Management: Data will be captured via REDCap (a free, secure, web-based application) and overseen by a data management and analysis team comprising statisticians at KNUST. Data will be reviewed on a bimonthly basis and issues will be communicated to the project coordinators for prompt resolution.

E.5. Data Safety Monitoring Board (DSMB): We will utilize a DSMB comprised of three experienced external experts (see letters), who will meet twice per year to review the study progress, safety, ethics, and outcomes.

[figure not shown]
E.6. PINGS-2 (Specific Aim 3)

Aim 3: To identify context-specific implementation facilitators and barriers, to understand the implementation context, and craft a theoretically-guided and evidence-based implementation strategies for routine use and policy adoption of the PINGS intervention in Ghana through multiple stakeholder engagements.

E.6.1 Study Design: Guided by the Normalization Process Theory (NPT), Community-based participatory research (CBPR) and NIH best practices for mixed methods research, we will conduct a mixed methods study to identify implementation barriers and facilitators, understand the implementation context and propose theory- or framework-guided implementation strategies for the PINGS intervention.

E.6.2. Theoretical underpinnings of PINGS Implementation strategy in Ghana: A greater use of explicit theory in order to understand barriers and facilitators, select implementation strategies and design interventions, has been advocated to advance implementation research.^{118,197}

The Normalization Process Theory (NPT) is a widely used^{198,199} theory of implementation that explains the process by which an intervention becomes, or indeed fails to become, normalized into routine practice.^{200,201} NPT is represented by four constructs namely *coherence* (the work that people do to understand and make sense of a practice), *cognitive participation* (the work that people do to engage and support a new practice), *collective action* (the work that people do to enact a new practice, and make it workable and integrate it in its context), and *reflexive monitoring* (the work that people do to reflect on and evaluate

enacting a new practice in context). We will also be draw on principles derived from the work by Grol and Wensing²⁰² to provide a systematic approach to implementation planning for the PINGS intervention.

E.6.3. Description of research plan to accomplish study aim 3 (refer to Figure 2): The PINGS Implementation Strategy Committee with representation from the Ghana Health Ministry, National Health Insurance, Local IT consultants, Hospital administrators, Clinicians (nurses and physicians from participating study sites, Stroke survivors and lay community members will be key stakeholders working with the PINGS taskforce in crafting an implementation strategy for the PINGS intervention in Ghana for specific aim 3.

E.6.3.1. Understanding the barriers & facilitators for implementation of PINGS: The Research team will undertake a systematic literature review on factors that influence the implementation of evidence-based mHealth based, self-management interventions for secondary prevention of CVDs after stroke in LMIC settings. Data from the review will be extracted and synthesized according to a Framework for Implementation (the Consolidated Framework for Implementation Research²⁰³) which categorizes implementation factors as relating to the intervention; the inner& outer contexts; the individual; or the process of implementation.

E.6.3.2. To develop a thorough understanding of the implementation context: To understand the context for

implementation of PINGS intervention into routine care in Ghana, we will engage key stakeholders including policy makers, implementers, Health providers at various cadres of service delivery & stroke survivors and family caregivers as end-users of the PINGS intervention. We will employ implementation methods such as concept mapping²⁰⁴ and group model building²⁰⁵ which are inherently participatory approaches with the potential of galvanizing stakeholders around common goals and creating consensus on implementation barriers.

E.6.3.3. To select theoretically informed and evidence based implementation strategies for PINGS: We will identify potential strategies from the Cochrane Effective Practice and Organization of Care (EPOC) taxonomy of implementation strategies.²⁰³ The evidence synthesis and assessment of the implementation context will inform the selection of the most suitable strategies to implement the PINGS intervention. Our selection of implementation strategies will be guided by the Normalization Process Theory, choosing strategies that would bring about change based on increasing coherence, cognitive participation, collective action and reflexive monitoring and its sub-domains. For each barrier identified at the patient, provider, health-system, and policy-level, we will propose implementation strategies following guidelines proposed by Proctor et al¹¹⁸.

E.6.3.4. Execution, evaluation and making adaptations to the implementation plan: The implementation strategies identified will be used to refine aspects of our proposed study before enrollment of study participants. We will perform assessments of acceptability, feasibility, fidelity and appropriateness of the PINGS intervention during the trial. Periodic meetings (twice each year) will be scheduled by the Implementation committee to discuss progress, trouble shoot challenges identified and co-create solutions.

E.6.4. Procedures: We will conduct **7 FGs (n=45-60 participants)** followed by **20 KIIs**. The FGs will last 60-90 minutes & the KIIs will last approximately 45-60 minutes & will occur at a location convenient to participants. A trained moderator will conduct the sessions with another member of the investigative team taking field notes during the session. Written consent will be obtained from participants prior to the start of any session. The purposive sample (based on demographics of the stroke survivors assigned to the PINGS intervention) for the FGs & KIIs (based on the clinical care providers (MDs, nurses, pharmacists, hospital administrators, policy makers) will be recruited through snowball techniques. **Survey data** will also be collected through self-filled questionnaires to be completed by stroke survivors on PINGS intervention (n=30) & healthcare workers involved in post-stroke care (n=20 from primary, secondary & tertiary medical facilities), health administrators & policy makers (n=10) after obtaining informed consent.

E.6.5. Data management and analyses: All FGs and KIIs will be digitally recorded and transcribed verbatim for qualitative analysis. All data will be uploaded and stored on REDCap, a secure data storage system. Transcripts of the audiotapes and field notes from the de-identified KIIs and FGs will be used for data analysis. The transcripts will be imported into the text analysis software (i.e. NVIVO²⁰⁶) for data management, & thematic analysis by the qualitative analyst. For the initial analysis of the data, the investigators will listen to the audio recordings and review the transcripts. The 'Framework Analysis' approach²⁰⁷ to be used includes five key stages: familiarization, identifying a thematic framework, indexing, charting, mapping, & interpretation. The investigative team will share findings by a process known as member checking²⁰⁸ with at least three FG and KII participants.

E.7. Training, Fidelity, and Compliance

E.7.1. Training: We will conduct training workshops for study coordinators and PINGS-2 providers at the beginning of the study. The workshop will be on study protocol, instruction in obtaining informed consent, filling out data collection forms, BP measurement, tasks and responsibilities of the study staff, education protocols, and patient flow. This training will consist of 3 full days in Year 1, and to prevent decay of skills, follow-up training sessions will be conducted every 12 months. The PINGS Task Force and the relevant study partners will provide oversight and ongoing supervision of training/coaching sessions, as well as random fidelity checks. To support fidelity of implementation, we will develop a comprehensive training manual (with step by step activities for implementation), provide orientation, training and return demonstration of procedures, and ongoing monitoring with checklist of steps (at least quarterly) with additional training as needed to support fidelity of implementation in both the health care and patient settings.

E.7.2. Patient Adherence with Protocol: Strategies to help ensure optimal levels of adherence include: (1) Stressing importance of attending all study visits; (2) Requesting names and telephone numbers of three friends and/or relatives who know how to reach the patient in the event we lose contact. *Several components of the PINGS interventions will also be administered in the preferred native language to enhance adherence.*

E.8. Anticipated Problems & Proposed solutions

E.8.1. Participant Accrual and Retention: We have chosen a one year primary time point to balance maximizing study follow up with studying a clinically useful time period of adherence. Multiple tactics will be used to facilitate high patient retention including obtaining full contact information for patients, caregivers, and relatives (e.g. identifiers of

location of residence for contact tracing, telephone numbers of patients and caregivers) at time of enrollment and updating every 3 months. Transportation will be provided for clinic visits.

E.8.2. Individual Randomization: We are randomizing patients instead of clusters, because it is the most statistically efficient method for showing efficacy & would require the smallest sample size.²⁰⁹ Cluster randomization is appropriate when contamination threat is high²¹⁰ but we believe contamination threat is minimal given that the Home BP monitor, protocol-based phone calls to nurse navigators, & educational audio messages will apply to the intervention group with a very low probability of the usual care group having access to all 3 components of the PINGS intervention.

E.9. Work Plan and Timetable: PINGS-2 is expected to last a total of 4.5 years from initiation of the first study site to completion of the last clinical trial participant. Activities in the first 9 months of Year 1 will include development of a detailed manual of operations, obtaining IRB and Ghana Foods and Drugs Authority approvals for the study protocol, setting up logistics, formation of a Data Safety Monitoring Board, development of a data management system, and training of study coordinators and nurses.

E.9.1. Pre-trial pilot testing of modified PINGS intervention: We will run a small pilot to pre-test the PINGS intervention among ≈ 10 stroke survivors (1 from each study site) for 1-month trial to trouble-shoot the intervention & make further modifications if required before starting the main trial by month 9 in year 1.

E.9.2. Recruitment & Follow-up of PINGS study: Anticipated *monthly* recruitment rate is ~1 participant (from each of 6 primary-level centers), 2 participants (from each of 2 secondary-level centers), up to 4 participants (at each of 2 tertiary-level centers) over 36 months will provide an estimated 648 participants (greater than 500 in the proposed study) for the clinical trial. Trial enrollment will be staggered by center, starting with two centers at a time, and for all centers initial recruitment targets for first few months lower than average targets to enable study sites get used to the trial processes and incorporate the study into their center. Recruitment will be stopped once the planned number of RCT participants is attained per site. The implementation strategy aims will start from year 1 through to year 5 to capture the change process during implementation. Data cleaning, final data analyses and manuscript preparation will take place in Months 54-60.

Table 4. Schedule of Activities

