C.6. Prelim Data #6: mHealth-based Med Adherence and BP Control in Ghanaian Stroke Patients: In a pilot RCT,^{44,45} we evaluated the feasibility of an mHealth technology-enabled, nurse guided intervention in improving BP control among 60 recent Ghanaian stroke survivors; 30 each in the intervention & standard of care (SC) arms. Participants in the intervention arm received a Blue-toothed UA-767Plus BT BP device & smart phone for monitoring, reporting BP measurements & med intake under nurse guidance for 3 months vs. SC. Tailored motivational text messages were delivered based upon levels of adherence to the medication intake. To control for attention exposure, the SC arm received SMS messages dealing with healthy lifestyle behaviors but not with med adherence. The PINGS intervention was stopped after month 3 & both groups were followed up until month 9. Primary outcome measure was BP control (<140/90mmHg at month 9). Secondary outcome measures included: (i) medication adherence measured using the Medication possession ratio (MPR) at month 9 and (ii) technological glitches. Outcomes: (1) BP control at month 3 by Intention to treat analysis was 20/30 (66.7%) vs 14/30 (46.7%), p=0.12 in the intervention and control arms respectively at interim analysis at end of intervention.⁴⁴ At month 9, proportion on the intervention vs. controls with systolic BP<140mmHg was 22/30(73.3%) versus 13/30(43.3%), p=0.035 in favor of the PINGS intervention.⁴⁵ (2) Medication possession ratio scores at month 3 were better in the intervention arm (0.88 ± 0.40) vs. SC (0.64 ± 0.45) arm (p=0.03), & at month 9 was (0.95 ± 0.16) vs (0.98 ± 0.24), p=0.56. These pilot trial findings support testing an mHealth intervention aimed at improving BP control after stroke in an under-resourced region.^{44,45} We observed a potential signal of efficacy with the intervention, which we have refined further to test within a larger definitive clinical trial in the current proposal.

D. SOLID COLLABORATIVE RESEARCH TEAM

Our interdisciplinary team has been involved in several projects of direct relevance to PINGS-2 research focus. Our interdisciplinary team represents experts in medicine, nursing, public health, health communication, and information technology. (see bios).

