E.4.1. Design: PINGS-2 is a phase III randomized, open label, blinded endpoint clinical trial to evaluate the efficacy and acceptability of a nurse-led, mHealth technology-centered, multi-level integrated approach in achieving sustained BP control among recent stroke survivors with hypertension encountered at primary, secondary and tertiary medical centers in Ghana, a LMIC in SSA compared with usual care. This is a 2-arm RCT involving 500 stroke survivors with individual participant randomization.

E.4.2. Eligibility: *Inclusion* – (i) age \geq 18 years (stroke is commoner above this age cut-off); (ii) male or females (sex is a biologic variable of interest); (iii) recent stroke (within one month of symptom onset)- stroke may be ischemic or hemorrhagic based on brain imaging or diagnosed clinically using the locally validated version of the 8-item questionnaire for verifying stroke free status (8-QVSFS) when neuroimaging is not feasible¹¹⁹; (iv) uncontrolled HTN (SBP \geq 140 mmHg at both the last clinical encounter post-stroke and the eligibility screening visit) - SBP is used as the selection variable since most African hypertensives <60 years have systolic or combination systolic/ diastolic HTN and for most patients, controlling SBP also results in DBP control;¹⁷⁰⁻¹⁷² (v) patients or family carers should own a basic mobile phone that can receive text/audio messages.

Exclusion – Any condition that would limit participation in follow up assessments, such as severe cognitive impairment/dementia (MMSE ≤ 24).

E.4.3. Training of Physicians and Nurse navigators on Standard of care for post-stroke vascular risk factor management using expert consensus guidelines: Physicians and nurse navigators at all 10 study sites will receive an initiation and annual training sessions on standard practices for post-stroke vascular risk factor management using local & current international guidelines¹⁷⁰ to be delivered by [name] (MPI) to minimize variability in provider practices across study sites and enhance patient safety.

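### For the primary endpoint the planned baseline-value covariate is a constant; adjustment for continuous baseline SBP and DBP should be prespecified

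*Combined protocol and SAP*

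**What the plan says.** **Entry.** Inclusion criterion (iv) in E.4.2 requires SBP of at least 140 "mmHg at both the last clinical encounter post-stroke and the eligibility screening visit". E.4.4 applies the same SBP-only threshold at screening. Two reasons are given. The first is that raised BP in Africans under 60 is mostly systolic or combined. The second is a clinical expectation: "and for most patients, controlling SBP also results in DBP control".

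**Endpoint.** E.4.8 sets the primary outcome as the proportion below 140/90 mmHg at 12 months. E.4.8.1 states "Uncontrolled BP is defined as average clinic systolic BP" of 140 or more, or diastolic of 90 or more, so either component alone makes a patient a failure. Table 3 lists BP at baseline and at months 3, 6, 9 and 12.

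**Analysis.** E.4.10.1 tests the hypotheses of Aims 1 and 2 with a linear mixed model of the 12-month outcome, with the baseline value as a covariate, adding other covariates that turn out imbalanced. The same section assigns binary outcomes to a generalized linear mixed model (GLMM) with a logit link. It compares the results with an analysis that leaves out the imbalance adjustment. It does not name SBP or DBP as covariates, and it gives no threshold for imbalance.

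**Pilot.** C.6 reports for month 9: "systolic BP<140mmHg was 22/30(73.3%) versus 13/30(43.3%), p=0.035 in favor of the PINGS intervention". E.4.9.2 reports, for the same visit, participants "with BP<140/90 mmHg at month 9 was 46% versus 40% after withdrawing the PINGS intervention after 3 months".

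**The concern.** A baseline covariate helps when it predicts the outcome. It then sharpens the comparison and removes the effect of chance differences at entry. For a binary endpoint built from two continuous measurements, the natural covariates are those two measurements at baseline. As written, the plan points to the baseline value of the outcome. Under the entry rule that value is the same for every participant.

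What remains is adjustment triggered by observed imbalance. That leaves the primary model unsettled until the data are seen, and baseline DBP enters only if someone judges it imbalanced. DBP is half of the endpoint and is not restricted at entry, so it can vary widely among participants. At stake are some precision, protection against chance differences in entry BP, and a primary model that is fixed in advance. The validity of the randomised comparison is not in question.

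**Working it through.** **1. The baseline value is constant.** Write control as C = 1 if SBP < 140 and DBP < 90, otherwise 0. Entry requires SBP ≥ 140, so C = 0 at baseline whatever the DBP. A patient at 142/74 and one at 160/105 both have C = 0. In a model with an intercept, a covariate equal to 0 for everyone has no estimable coefficient and changes nothing. This assumes that the screening BP serves as the baseline BP. If baseline were a separate reading, a few patients might fall below 140/90 and the covariate would be nearly constant rather than exactly so.

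**2. The other rule need not bring DBP in.** Adjustment depends on observed imbalance. DBP enters if it is judged imbalanced and stays out otherwise, even though a predictive covariate is worth including in either case.

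**3. Reproducing the plan's figures.**
- Pilot SBP result: Fisher's exact test on 22/30 versus 13/30 gives p = 0.0352, matching the stated 0.035.
- Sample size: 60% versus 44%, two-sided alpha 0.05, power 90%, pooled variance and no continuity correction give 203 per arm, 406 in total, as stated. This is an unadjusted calculation on the joint endpoint, so the requested adjustment does not disturb it.

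**4. How much DBP can matter.** The inputs are 22/30 and 13/30 with SBP < 140 (C.6), and 46% and 40% with BP < 140/90 (E.4.9.2, no counts given). On 30 per arm, 0.46 × 30 = 13.8, read as 14, and 0.40 × 30 = 12. Patients below 140/90 are a subset of those with SBP < 140, so the difference is the number with SBP < 140 but DBP ≥ 90.

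| | SBP < 140 | BP < 140/90 | SBP < 140, DBP ≥ 90 | Both controlled, among SBP-controlled (exact 95% CI) |
|---|---|---|---|---|
| Intervention | 22 | 14 | 22 − 14 = 8 (8/22 = 36%) | 14/22 = 64% (41–83%) |
| Usual care | 13 | 12 | 13 − 12 = 1 (1/13 = 8%) | 12/13 = 92% (64–100%) |
| Pooled | 35 | 26 | 9 (9/35 = 26%) | 26/35 = 74% (57–88%) |

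The difference between arms is 73.3 − 43.3 = 30.0 points on SBP alone. On the joint endpoint it is 46 − 40 = 6 points, or 46.7 − 40.0 = 6.7 points with the counts above (Fisher p = 0.79). Of the net 22 − 13 = 9 extra intervention patients with SBP control, a net 14 − 12 = 2 also had joint control.

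**5. Sensitivity.** 14/30 is 46.7%, so 46% would be truncated rather than rounded. If 46% were 13/28, joint control among the SBP-controlled would be 13/22 = 59%, still a majority.

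**The case against.** **The pilot contradicts the rationale.** A reader might infer this. The documents do not support it: the claim is about most patients, and 14/22, 12/13 and 26/35 are all majorities. The intervention-arm interval (41–83%) includes 50%, so support there is weak, but weak support is not contradiction. No pilot DBP data are reported. The counts combine figures from two sections whose analysis sets may differ. The apparent concentration of DBP failure in the intervention arm (8/22 versus 1/13) has Fisher p = 0.11. Both figures were taken six months after the pilot intervention stopped, whereas PINGS-2 delivers it for 12 months.

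**The entry rule conflicts with the endpoint.** This is also tempting, and also unsupported. SBP ≥ 140 is a subset of the E.4.8.1 definition, so every enrolled patient is uncontrolled under both. The rule leaves out only isolated diastolic hypertension. That is a permissible population choice with a second stated reason, and it does not bias the comparison between arms.

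**The baseline-value sentence is about a linear model.** It is, and binary outcomes are assigned a logit-link GLMM. But the sentence says it tests Aim 1, whose primary outcome is binary, and the GLMM text names no baseline BP covariate. On either reading, the primary comparison has no working baseline BP adjustment fixed in advance.

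**Imbalance is already covered.** A visible imbalance in DBP would be adjusted for, and the test's error rate already allows for chance imbalance. Both points stand. They limit the issue to precision and prespecification, and do not remove it.

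**Conclusion.** The point holds as an analysis-specification gap. For the binary primary outcome the named baseline covariate is constant, and adjustment for baseline DBP is left to a data-dependent rule. The conclusion rests on the entry and endpoint definitions, taking screening BP as baseline.

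The pilot arithmetic shows only that DBP can decide a material share of joint outcomes: about 8 of 22 SBP-controlled intervention patients and 1 of 13 controls, with the arm difference falling from 30 to about 6 to 7 points. It assumes 30 per arm for both measures and 46% read as 14/30. The gain in precision cannot be computed, because the documents give no association between baseline BP and 12-month control. Nothing here requires a change to criterion (iv) or removal of its rationale.

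**What to change.** In E.4.10.1, state that the primary comparison of BP < 140/90 mmHg at 12 months uses a logistic model, or a logit-link GLMM, adjusted for continuous baseline SBP and continuous baseline DBP. These replace the constant baseline status and are included whatever imbalance is observed. Keep the unadjusted comparison that the plan already promises beside it. Report the proportions with SBP < 140 and with DBP < 90 separately by arm, next to the joint endpoint.

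The cost is a sentence or two in the analysis section and two extra rows in the results table. BP is already measured at baseline and at each follow-up visit, so no new data are needed, and the sample size stands. The adjusted odds ratio is conditional on baseline BP and should be labelled so. SBP-only entry may stay.
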